2.2 Safety

The safety population is:

All randomised subjects with at least a partial dose of study medication.

Subjects will be assessed according to the treatment received.

2.3 Pharmacokinetics

Not applicable.

2.4 Other populations

2.4.1 Screened population

The screened population is:

All subjects screened (i.e. who signed the informed consent).

23/62

F-FR-58800-003

2.5 **Primary populations**

The primary analysis based on the primary efficacy endpoint will be performed on the mITT population. In that analysis, subjects who do not undergo colonoscopy because of inadequate preparation or preparation-related AEs will be considered as failures. In addition, robustness of primary efficacy results will be assessed by repeating the primary analysis on the PP population.

The analyses of safety data will be performed based on the safety population.

3 STATISTICAL METHODS

3.1 Statistical analysis strategy

The statistical analyses will be performed in accordance with ICH E9 guideline [3], will be based on the pooled data from the individual study sites, unless otherwise stated, and will be performed by Biotrial Biometrics, France, managed by the sponsor's Biometry Department.

Statistical evaluation will be performed using Statistical Analysis System (SAS)[®] (version 9.4 or higher) [4]

3.1.1 Primary efficacy endpoint

The primary efficacy endpoint is the proportion of subjects with a successful overall preparation (i.e. graded as excellent (4) or good (3) based on a 4-point scale).

3.1.2 Secondary efficacy endpoints

The secondary efficacy endpoints are:

- the need to place a nasogastric tube to complete preparation,
- the time to clear effluent (from first intake of preparation), as reported by the subject,
- the need for rescue treatment (saline enema) because of inadequate preparation,
- the colon cleansing scores assessed by the 4-point scale (poor, fair, good, excellent),
- the overall and segmental cleansing scores assessed by BBPS,
- the time to caecal intubation (from colonoscope introduction to caecal intubation),
- the duration of examination, measured by colonoscope withdrawal time from caecum,
- the procedure documented as completed (procedures that reached the caecum),
- the treatment compliance: volumes of fluids measured by the caregiver and reported in the treatment questionnaire of subject's leaflet during treatment administration,
- the treatment acceptability, assessed by a Treatment Acceptability Questionnaire completed by the caregiver or the subject at the time of intake using a 5-point scale questionnaire to be filled in immediately after dosing,
- the time between the last intake of fluids and the start of colonoscopy procedure.

3.1.3 Safety endpoints

The safety endpoints are:

- Collection of adverse events (AEs) (for up to 30 days following the day of colonoscopy (collected at Visit 4 Day 32 -5/+15));
- Tolerability of the preparation by a Symptom Scale after each dose of treatment rated by the subjects on related symptoms after intake (stomach cramping, stomach bloating and nausea) on a paediatric 5-point scale, ranging from 1=no symptom to 5= severely distressing symptoms;

- Description and histological examination of any colonic biopsy specimens of mucosal lesions suspected by the investigator to have been caused by colonic lavage;
- Vital signs including body weight and temperature, systolic and diastolic BP and HR;
- Local laboratory data: serum and urinary biochemistry, at baseline, at colonoscopy and at the end of study;
- Blood and urine sulfates assessed at central laboratory.

3.1.4 Multiplicity

No adjustment for multiple testing is planned in this study, since the primary endpoint of treatment success will be tested sequentially (hierarchical structure) with the first test being non-inferiority test based upon the treatment difference. A rejection of the null hypothesis will trigger superiority testing based upon the treatment difference, so that the second test (superiority) will only be considered if the first test (non-inferiority) is accepted.

3.1.5 Significance testing and estimation

The primary endpoint of treatment success will be tested sequentially with the first test being a non-inferiority test based upon the treatment difference.

A two-sided 95 % confidence interval (CI) for the difference of the two clinical success rates (Eziclen®/Izinova® minus Klean-Prep®) will be calculated. If and only if the lower limit of the CI is greater than the lower limit of equivalence region -15%, Eziclen®/Izinova® will be proven to be not less effective than Klean-Prep®.

A rejection of the null hypothesis will trigger superiority testing based upon treatment difference. If the lower limit of the CI is greater than zero, Eziclen®/Izinova® will be proven to be superior to Klean-Prep®.

The secondary endpoints will be tested for descriptive purpose only.

3.2 Analysis methods

Descriptive statistics will be presented as follows:

- Continuous variables: number of observations, number of missing data, mean, standard deviation (SD), median, quartiles, minimum and maximum;
- Dichotomous or categorical variables: frequency and percentage of each of the categories and number of missing data.

All study data will be at least presented in listings.

3.2.1 Efficacy

The primary efficacy analysis will be performed on the mITT population as well as on the PP population to assess the robustness of the results. The secondary efficacy analyses will be performed on the ITT population and repeated on the mITT and PP if they differ from ITT from more than 10 %. The other efficacy analyses will be performed on the ITT population and repeated on the mITT from more than 10 %.

3.2.1.1 Primary efficacy analyses

The primary endpoint of treatment success will be tested sequentially (hierarchical structure) with the first test being non-inferiority test based upon the treatment difference. A rejection of the null hypothesis will trigger superiority testing.

The two hypothesis tests are hierarchically structured so that the second test (superiority) will only be considered if the first test (non-inferiority) is accepted. The superiority test is powered

to detect an absolute difference of 18 %. There is no alpha adjustment for the second test as a result of the hierarchical testing.

The primary efficacy analysis will be based on the mITT population and repeated on the PP population in order to assess the robustness of the results.

The primary efficacy variable is the proportion of subjects with successful overall preparation evaluated with the scale (from 1 to 4) of the Cleansing Score as assessed by the colonoscopist.

A successful preparation will be defined as excellent (4) or good (3) preparation.

A failure preparation will be defined as:

- Fair (2) or poor (1) according to colon cleansing score,
- Any subject who did not have a colonoscopy based on the investigator's assessment of the cleansing (insufficient faecal output, unclear faecal discharge, etc.) or due to preparation related AEs,
- Any subject for whom cleaning was not adequate for evaluation,
- Any subject for whom rescue treatment (saline enema) was needed.

The proportion of subjects with successful colon cleansing (graded as excellent or good) will be summarised along with the 95 % CI using the standard Wald asymptotic CI using the following SAS code:

```
proc freq data=ADCC(where=(PARAM='Successful overall preparation' and MITTFL='Y'));
```

```
table AVALC / missing binomial(level='Yes' cl=wald);
```

by TRTP;

run;

The primary efficacy endpoint will be analysed using a logistic regression model including treatment and country as covariates as well as the interaction between treatment and country if it is significant (i.e. p < 0.10, as interaction tests have low power) using the following SAS code providing the adjusted proportions with their 95 % CI thank to ilink option, and with the option firth in the model with interaction since there might otherwise be a quasi-complete separation of data points affecting the validity of the model:

proc logistic data=ADCC(where=(PARAM='Successful overall preparation' and MITTFL='Y'));

class TRTP(ref='KLEAN-PREP') COUNTRYC(ref='Largest country') / param=glm;

model AVALC(EVENT='Yes') = TRTP COUNTRYC TRTP*COUNTRYC /
link=logit firth;

lsmeans TRTP / cl ilink;

ods output lsmeans=lsm ModelANOVA=TestInter;

run;

N.B.: TRTP*COUNTRYC, firth and ModelANOVA=TestInter will be removed if the interaction is not significant.

The formal hypothesis test result (p-value) for treatment difference will be presented together with a two-sided 95 % CI for the treatment difference in success rates. The non-inferiority will be demonstrated if the lower limit of the 95 % CI of that difference is higher than -15 %. The treatment difference and its p-value assessed for -15 % margin will be estimated using the

26/62

following SAS code, since the logistic procedure does not provide adjusted treatment differences:

proc freq data=ADCC(where=(PARAM='Successful overall preparation' and MITTFL='Y'));

table TRTP / nopercent norow nocum;

ods output OneWayFreqs=TRTfreq;

run;

data estimates;

merge TRTfreq lsm; by TRTP; AVALC="N"; Count=Frequency*(1-Mu); output; AVALC="Y"; Count=Frequency*Mu; output; keep TRTP Frequency Mu AVALC Count;

run;

proc freq data=estimates order=data;

table TRTP*AVALC / alpha=0.05 riskdiff(noninf margin=0.15 column=2); weight Count; ods output PdiffNoninf=NonInf;

run;

If the non-inferiority is demonstrated, the superiority will be analysed based upon treatment difference. If the lower limit of the CI is greater than zero, Eziclen®/Izinova® will be proven to be superior to Klean-Prep®. The following SAS code will be used to get the superiority p-value:

```
proc freq data=estimates order=data;
table TRTP*AVALC / alpha=0.05 riskdiff(sup column=2);
weight Count;
ods output PdiffSup=Sup;
```

run;

A robustness analysis of primary efficacy results will be assessed by repeating the primary analysis on the PP population.

Furthermore, the robustness of the results will be assessed by using another SAS procedure in the mITT, since the adjusted difference cannot be assessed directly from the proc logistic inducing a potential bias. Then the SAS procedure genmod will be used with identity link including treatment and country as covariates, using the following example of SAS code:

proc genmod data=ADCC(where=(PARAM='Successful overall preparation' and MITTFL='Y')); class TRTP(ref='KLEAN-PREP') COUNTRYC(ref='Largest country');

class TRTP(ref='KLEAN-PREP') COUNTRYC(ref='Largest country'); model AVALC(EVENT='Yes') = TRTP COUNTRYC / link=identity; lsmeans TRTP / diff cl;

run;

No p-value will be displayed for the genmod model, since this would not be equivalent to the ones provided for the logistic procedure analysis.

In addition, the robustness of the results will be assessed in the mITT population by repeating the procedure logistic and estimating the 95 % CI of the treatment difference using the bootstrap method:

- The adjusted proportions will be estimated using the proc logistic model;
- 10'000 random samples will be generated using a proc surveyselect from the observed data with treatment and country as stratification and with seed=111;
- The adjusted proportions for each sample will be estimated using the same proc logistic model by replicate;
- The treatment differences will be derived for each sample;
- The 2.5 and 97.5 percentiles of the 10'000 estimated treatment differences will be considered for the 95 % CI of the treatment difference.

The following SAS code will be used:

```
proc logistic data=ADCC(where=(PARAM='Successful overall preparation' and
MITTFL='Y'));
    class TRTP(ref='KLEAN-PREP') COUNTRYC(ref='Largest country') /
    param=glm;
    model AVALC(EVENT='Yes') = TRTP COUNTRYC / link=logit firth;
    lsmeans TRTP / cl ilink;
    ods output lsmeans=lsm;
```

run;

proc transpose data=lsm out=_lsm;

var Mu; id TRTP;

run;

data diff;

```
set _lsm;
diff = EZICLEN - KLEAN-PREP;
```

run;

```
proc surveyselect data=ADCC(where=(PARAM='Successful overall preparation' and MITTFL='Y')) out=samples method=urs samprate=1 rep=10000 outhits seed=111; strata TRTP COUNTRYC;
```

run;

proc sort data=samples; by replicate; run;

proc logistic data=samples;

by replicate;

class replicate TRTP(ref='KLEAN-PREP') COUNTRYC(ref='Largest country') /
param=glm;
model AVALC(EVENT='Yes') = TRTP COUNTRYC / link=logit;
lsmeans TRTP / cl ilink;

ods output lsmeans=lsm_boot(keep=replicate TRTP Mu);

run;

```
proc sort data=lsm_boot; by replicate; run;
proc transpose data=lsm_boot out=_lsm_boot;
      var Mu;
      by replicate;
      id TRTP;
run;
data final;
      set _lsm_boot;
      diff = EZICLEN - KLEAN-PREP;
run;
proc sort data=final; by diff; run;
```

proc univariate data=final noprint;

var diff;

output out=ci95(rename=(Q2_5=Lower Q97_5=upper Q50=median)) pctlpre=Q pctlpts=2.5 50 97.5;

run;

No p-value will be displayed for this robustness analysis.

Finally, primary efficacy results will be repeated in the mITT by country using the main model with the treatment * country interaction in order to get the treatment effect by country as follows:

proc logistic data=ADCC(where=(PARAM='Successful overall preparation' and MITTFL='Y'));

class TRTP(ref='KLEAN-PREP') COUNTRYC(ref='Largest country') /
param=glm;
model AVALC(EVENT='Yes') = TRTP COUNTRYC TRTP*COUNTRYC /
link=logit firth;
lsmeans TRTP*COUNTRYC / cl ilink;

run;

The adjusted proportions by country with their 95 % CI and the treatment difference with their 95 % CI derived using proc freq as above by country will be presented, but p-values will not be displayed.

And primary analysis will also be repeated in the mITT by age class, weight class and sex using the main model with the treatment * country interaction if it is significant in the primary model, as well as the treatment * subgroup interaction as follows:

proc logistic data=ADCC(where=(PARAM='Successful overall preparation' and MITTFL='Y'));

class TRTP(ref='KLEAN-PREP') COUNTRYC(ref='Largest country') SUBGROUP(ref='First class') / param=glm;

model AVALC(EVENT='Yes') = TRTP COUNTRYC TRTP*COUNTRYC TRTP*SUBGROUP / link=logit firth;

lsmeans TRTP*SUBGROUP / cl ilink;

The adjusted proportions by subgroup with their 95 % CI and the treatment differences with their 95 % CI will be presented, but p-values will not be displayed.

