# **10.2** Sample Size Determination

The primary aim of the study is to show that Eziclen®/Izinova® is not inferior to Klean-Prep® in the proportion of subjects with successful colon cleansing.

A non-inferiority margin of 15% has been selected for consistency with other studies in colon cleansing preparations.

Therefore assuming a success rate (excellent or good response) of 85% in both the Eziclen®/Izinova® and Klean-Prep® groups, a one-sided alpha of 0.025 and 90% power, 120 subjects are required per treatment group. Assuming a rate dropout/non-compliance to protocol of 4% based on previous studies and taking into account that subjects will be hospitalised for treatment administration, 125 subjects will be randomised in each treatment group, i.e. 250 subjects in total. Enrolment will be completed once 250 subjects have been randomised.

The primary endpoint of treatment success will be tested sequentially (hierarchical structure) with the first test being non-inferiority test based upon the treatment difference. A rejection of the null hypothesis will trigger superiority testing based upon the treatment difference.

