#### 10.4.5 Efficacy Evaluation

As indicated in Section 7.1, the primary efficacy variable is the proportion of subjects with successful overall preparation evaluated with the scale (from 1 to 4) of the Cleansing Score as assessed by the colonoscopist.

A successful preparation will be defined as excellent (4) or good (3) preparation.

A failure preparation will be defined as:

- Fair (2) or poor (1) according to bowel cleansing
- Any subject who did not have a colonoscopy based on the investigator's assessment of the cleansing (insufficient faecal output, unclear faecal discharge, etc.) or due to preparation related AEs.
- Any subject for whom cleaning was not adequate for evaluation.
- Any subject for whom rescue treatment (saline enema) was needed.

The proportion of subjects with successful colon cleansing (graded as excellent or good) will be summarised along with the 95% confidence interval (CI) using the standard Wald asymptotic CI. The primary efficacy endpoint will be analysed using a logistics regression model including country as stratified variable, the interaction between country and treatment will be also investigated. The formal hypothesis test result (p-value) for treatment difference will be presented together with a two-sided 95% CI for the difference in success rates. The non-inferiority will be demonstrated if the lower limit of the 95% CI of that difference is higher than -15%.

If the non-inferiority is demonstrated, the superiority will be analysed based upon treatment difference. If the lower limit of the CI is greater than zero, Eziclen®/Izinova® is proven to be superior to the Klean-Prep®.

Secondary efficacy endpoints are presented in Section 7.2.

Results will be tabulated by treatment group and overall using descriptive summary statistics (mean SD, median, interquartiles and ranges) or frequency count with two-sided 95% CI when appropriate.

Time to clear effluent data will be analysed by using survival methods. The results will be presented both in summary tables (number of events, censors, median and interquartile time to event with 95% CI...) and graphically in Kaplan-Meier plots by treatment group and overall. This will be detailed in the SAP.

Other secondary endpoints will be analysed using Cochran-Mantel-Hænszel (CMH) chi-square for count (percentage) adjusting for country effect and two-way analysis of variance (ANOVA) for continuous parameters including treatment, country and their interaction as covariates.

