1.4.4 Planned sample size

The primary aim of the study is to show that Eziclen®/Izinova® is non-inferior to Klean-Prep® in the proportion of subjects with successful colon cleansing.

A non-inferiority margin of 15 % has been selected for consistency with other studies in colon cleansing preparations.

Therefore assuming a success rate (excellent or good response) of 85 % in both the Eziclen®/Izinova® and Klean-Prep® groups, a one-sided alpha of 0.025 and 90 % power, 120 subjects are required per treatment group. Assuming a rate dropout/non-compliance to protocol of 4 % based on previous studies and taking into account that subjects will be hospitalised for treatment administration, 125 subjects will be randomised in each treatment

22/62

group, i.e. 250 subjects in total. Enrolment will be completed once 250 subjects have been randomised.

The primary endpoint of treatment success will be tested sequentially (hierarchical structure) with the first test being non-inferiority test based upon the treatment difference. A rejection of the null hypothesis will trigger superiority testing based upon the treatment difference.

The two hypothesis tests are hierarchically structured so that the second test (superiority) will only be considered if the first test (non-inferiority) is rejected. The superiority test is powered to detect an absolute difference of 18 %. There is no alpha adjustment for the second test as a result of the hierarchical testing.

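### The interval that decides non-inferiority has no named method and appears to be Wald; on raw counts its one-sided error is 2.6% at the planned 85% Klean-Prep rate and 3.6% at 97%, against a stated 2.5%.

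*SAP*

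**What the plan says.** SAP 3.2.1.1 treats the primary result in two steps.

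- **Rate in each arm.** The proportion of successes "will be summarised along with the 95 % CI using the standard Wald asymptotic CI using the following SAS code". Protocol 10.4.5 likewise summarises it "using the standard Wald asymptotic CI". This is a description of each arm.
- **Difference between arms.** Non-inferiority is shown if the lower limit of the two-sided 95% interval for Eziclen minus Klean-Prep lies above -15%. The code converts country-adjusted proportions from the logistic model back into counts and passes them to a frequency procedure with "alpha=0.05 riskdiff(noninf margin=0.15 column=2". No interval method appears in that option list. The surrounding text, SAP 3.1.5 and Protocol 10.3 name none either.

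The error the rule should deliver is given in SAP 1.4.4 as "a one-sided alpha of 0.025 and 90 % power", and Protocol 10.2 says the same. SAP 3.2.1.1 also plans an identity-link model and a bootstrap percentile interval for the difference, both as robustness analyses.

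**The concern.** Wald is the only interval method named for the primary endpoint, and the code for the difference asks for nothing else. The natural reading is that the -15% decision rests on a Wald limit.

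A Wald limit estimates the variance at the observed rates. When the comparator rate is close to 100%, that variance is often too small and the lower limit sits too high. A truly inferior product then passes more often than the nominal rate allows. At stake is whether the stated one-sided 0.025 holds, and whether a borderline result could turn on an interval formula that the plan does not name.

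**Working it through.** **Inputs.** Protocol 10.2 gives one-sided alpha 0.025, 90% power and 120 evaluable per arm, "assuming a success rate (excellent or good response) of 85% in both the Eziclen®/Izinova® and Klean-Prep® groups". It also gives the margin ("A non-inferiority margin of 15% has been selected for consistency with other studies in colon cleansing preparations") and 4% dropout, leading to 125 randomised per arm.

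**The plan's own figure.** n = (1.960 + 1.282)² × (0.85×0.15 + 0.85×0.15) / 0.15² = 10.507 × 0.255 / 0.0225 = 119.1, so 120 per arm. Then 120 / 0.96 = 125. Both match. This formula uses the unpooled (Wald) variance.

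**Rules compared, on raw counts.** Let E and K be the observed success rates, n the number per arm and N = 2n.

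- Wald: pass if E − K − 1.96 × √{[E(1−E) + K(1−K)]/n} > −0.15.
- Score (Miettinen-Nurminen): pass if (E − K + 0.15) / √{[e(1−e) + k(1−k)]/n × N/(N−1)} > 1.96, where e and k are the maximum-likelihood rates under e = k − 0.15.

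All pairs of counts are enumerated. The error is the probability of passing when the true Eziclen rate is exactly 15 points below the Klean-Prep rate.

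| Klean-Prep rate | Wald, n=120 | Score, n=120 | Wald, n=125 | Score, n=125 |
|---|---|---|---|---|
| 75% | 2.43% | 2.52% | 2.52% | 2.56% |
| 80% | 2.51% | 2.53% | 2.55% | 2.53% |
| 82% | 2.53% | 2.52% | 2.59% | 2.52% |
| 85% | 2.61% | 2.50% | 2.64% | 2.49% |
| 90% | 2.82% | 2.39% | 2.73% | 2.50% |
| 95% | 3.23% | 2.34% | 3.17% | 2.36% |
| 97% | 3.58% | 2.14% | 3.64% | 2.25% |

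**Power at 85% in both arms.** With 120 per arm, Wald gives 90.4% and score 89.1%. With 125, Wald gives 91.3% and score 90.6%.

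**Example where the formula changes the conclusion.** Take 107/125 (85.6%) against 116/125 (92.8%).

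- Difference: −0.072.
- SE: √[(0.856×0.144 + 0.928×0.072)/125] = √(0.19008/125) = 0.0390.
- Wald lower limit: −0.072 − 1.96×0.0390 = −14.8%, which passes.
- Score z: 1.89, below 1.96, which fails.

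At 125 per arm, 26 outcome tables pass under Wald and fail under score. Of these, 13 have both arms at 24% success or lower and have no bearing here; the other 13 have Klean-Prep at 101/125 or higher. Two tables go the other way. At 120 per arm the counts are again 26 (13 of them at high success rates), with 10 the other way.

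**Arm-level 95% coverage, n=120.** Wald covers 93.9% at 85% success, 91.9% at 93%, 85.4% at 96% and 87.5% at 97%. Wilson covers 94.6% at 85% and 97.1% at 97%.

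**The SAP's adjusted counts.** The table above does not describe these. The no-interaction branch was simulated at 120 per arm with Wald limits on the rebuilt counts. The documents give no country sizes, so the splits are assumptions. With four equal countries the error was 2.8% at 85% and 5.6% at 97%. Three uneven splits gave 3.0% to 7.3% at 85%. Replacing Wald with score on these counts lowered the error in every split tried but did not fully restore 2.5%.

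**The case against.** The strongest reply is that little is at stake where this trial is likely to sit. The excess is 0.1 point at the planned 85%. Protocol 1.3 reports 82.4% and 80.3% success in the adult 1-day study, and 81% and 83% in the adolescent study; at such rates Wald and score are practically the same. At 75% with 120 per arm the score rule errs slightly more than Wald. Rates of 96-97% appear only in the adult split-dose study, whereas this trial uses a 1-day regimen. All of this stands, and it is why the point is minor.

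Some stronger readings are tempting but not supported:

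- **That the plan specifies Wald for the decision.** It names Wald only for the arm-level rates. For the difference, Wald is inferred from the absence of a method option.
- **That success above 90% (Protocol 1.4) puts the trial where the error is largest.** That figure is for Eziclen in adults, pooled over regimens. The error depends on the Klean-Prep rate: with Eziclen truly above 90%, the boundary would need Klean-Prep above 105%.
- **That Wald always favours non-inferiority.** At 75% with 120 per arm it does not.
- **That the arm-level coverage undermines the conclusion.** Those intervals are descriptive and decide nothing.

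The bootstrap interval is a useful check that does not rely on a Wald limit, but it is supportive and leaves the decision interval as it is.

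**Conclusion.** The point holds in a limited form. The method for the interval that decides the trial should be named, and a score-type interval keeps the stated error better than Wald when the comparator does well. On raw counts with 120 per arm, the Wald excess over 2.5% is 0.1 point at a Klean-Prep rate of 85%, 0.3 at 90%, 0.7 at 95% and 1.1 at 97%, and essentially nil at 80-82%.

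This rests on two assumptions: that the code as written yields a Wald limit, and that raw counts stand in for the country-adjusted ones. A reader might take 2.6% to 3.6% as the error of the SAP's actual procedure. It is not. That procedure also carries error from country weighting, whose size depends on country splits that the documents do not give and which needs separate treatment. This is a cheap improvement, not a threat to the trial's conclusion at the planned rates.

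**What to change.** In SAP 3.2.1.1 and Protocol 10.4.5:

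- Name a Miettinen-Nurminen (score) two-sided 95% interval as the decision interval for the difference. Request it explicitly in the code and keep the Wald interval as supportive.
- Use Wilson limits for each arm's success rate.
- State how the score interval is applied to the country-adjusted estimate. Changing the method on the rebuilt counts reduces the error but leaves the country-weighting part untouched.

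The first two items cost a sentence each and an option in the code; the third needs a short specification. The price is power at 85% in both arms: 1.3 points with 120 per arm (90.4% to 89.1%, just under the 90% target) and 0.7 points if all 125 are evaluable (91.3% to 90.6%).

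### A treatment-by-country pre-test at p<0.10 chooses the primary model and its CI; when it fires and country sizes are clearly unequal, non-inferiority is declared too easily

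*SAP*

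**What the plan says.** Protocol 10.4.5 specifies a logistic regression with country as a stratification variable and adds that "the interaction between country and treatment will be also investigated". It gives no rule by which that investigation changes the primary model.

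SAP 3.2.1.1 goes further. The interaction enters the primary model "if it is significant (i.e. p < 0.10, as interaction tests have low power". A note under the code adds that "TRTP*COUNTRYC, firth and ModelANOVA=TestInter will be removed if the interaction is not significant". The test therefore switches both the interaction term and the Firth penalty on or off.

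The adjusted success rates come from "lsmeans TRTP / cl ilink", with no weighting option. Each rate is multiplied by the full arm size to make pseudo-counts, and PROC FREQ computes the difference and its CI from that 2x2 table. The decision rule is: "The non-inferiority will be demonstrated if the lower limit of the 95 % CI of that difference is higher than -15"%. The superiority step uses the same pseudo-count table.

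SAP section 5 lists the keep-if-significant rule as a protocol change for the secondary ANOVAs. It refers to the primary analysis only by analogy and does not list it as a change there. The SAP's change log does record it for the primary model.

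**The concern.** Two things go wrong together.

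- **The quantity estimated depends on the data.** Without the interaction, the model has one common treatment effect. With it, the LS-means average the countries equally on the logit scale, so a country with 15 subjects per arm moves the estimate as much as one with 70. Neither document says which average is the target.
- **The CI does not match the estimate.** Pseudo-counts carry the variance of a simple proportion on the whole arm, Mu(1-Mu)/N. An equal-country average of unequal countries is less precise than that, and the model's own standard error is discarded.

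The trial has one confirmatory decision, and it also opens the superiority test. If it comes from the interaction branch, a few subjects in small countries could carry the lower limit past -15 points, with a CI that hides their imprecision.

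**Working it through.** **Inputs from the documents.** Success 85% in both arms, margin 15 points, one-sided alpha 0.025, power 90%, 120 per arm, 125 after 4% dropout (Protocol 10.2, SAP 1.4.4). Allocation 1:1, stratified by country (Protocol 3.3). Around 25 centres (Protocol 3.1).

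**Assumptions.** The number and size of countries are not given. The only hint is that the code takes the largest country as reference level. I assume 2 to 5 countries, from equal to clearly unequal. The null is 70% vs 85%.

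**1. The plan's own figure.** n = (1.960+1.282)² x (2 x 0.85 x 0.15) / 0.15² = 10.51 x 0.255 / 0.0225 = 119.1, so 120 per arm; 120/0.96 = 125. Power at 120 is 90.2%. The figure reproduces, but for a pooled comparison with no model selection.

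**2. Standard error in the interaction branch.** The SAP's SE is about √[(0.70x0.30 + 0.85x0.15)/120] = √(0.3375/120) = 0.053 for any layout. For an equal-country logit average with n_k per arm in each of K countries, the delta method gives Mu(1-Mu) x Σ(1/n_k)/K². The effective arm size is therefore K²/Σ(1/n_k):

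- 40/40/40: 9/0.0750 = 120, SE 0.053 (no loss)
- 50/40/30: 9/0.0783 = 115, SE 0.054
- 70/35/15: 9/0.1095 = 82, SE 0.064
- 60/35/15/10: 16/0.2119 = 76, SE 0.067

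Selecting trials with a significant interaction widens the spread further. In simulated fired trials at 70/35/15, the estimate has SD 0.078 against a mean SAP SE of 0.053. Its mean is -13.2 points, not -15.

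**3. Whole procedure, common -15-point difference.** 150,000 simulated trials per layout followed the SAP steps: Firth cell rates (y+0.5)/(n+1), Wald interaction test at 0.10, LS-means from the selected model, pseudo-counts, 95% Wald lower limit against -15%. All results are percentages. The last column is a country-stratified Mantel-Haenszel-weighted risk difference with its own stratified variance.

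| Per arm by country | Test fires | False NI when fired | SAP overall | Additive model only | Stratified RD |
|---|---|---|---|---|---|
| 60/60 | 9.0 | 2.7 | 2.6 | 2.6 | 2.5 |
| 40/40/40 | 7.4 | 3.0 | 2.7 | 2.7 | 2.6 |
| 24 x 5 | 3.9 | 3.6 | 2.7 | 2.7 | 2.6 |
| 50/40/30 | 7.1 | 4.3 | 2.8 | 2.7 | 2.5 |
| 40/35/25/20 | 5.3 | 5.3 | 2.9 | 2.7 | 2.6 |
| 90/30 | 8.1 | 13.4 | 3.7 | 2.8 | 2.6 |
| 70/35/15 | 6.0 | 13.7 | 3.7 | 3.0 | 2.5 |
| 60/35/15/10 | 3.9 | 15.5 | 4.2 | 3.7 | 2.5 |
| 50/30/20/12/8 | 2.9 | 13.3 | 5.0 | 4.7 | 2.6 |

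Repeat runs put the clearly unequal layouts at about 12-17% when fired and 3.6-5% overall. Extreme imbalance is worse: 100/10/10 gives 6.1% overall, against 4.8% with the additive model alone.

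**4. Separating the causes.** On the same fired trials at 70/35/15 (40,000 simulated), false non-inferiority is 12.9% with the interaction model and 2.1% with the additive one, so the switch matters. Replacing the pseudo-count SE by the model-based SE cuts 13.7% to 6.0%, so much of the harm is the variance. The additive column also exceeds 2.5%, because that branch uses the same equal weighting and pseudo-counts.

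**5. Effects that differ by country, patient-weighted difference -15.** Layout 80/20/20:

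- Small countries better, -18/-10/-8: (80x-18 + 20x-10 + 20x-8)/120 = -15. The equal-country mean is -12. Overall error is about 8%, against 3.9% without the pre-test.
- Small countries worse, -12/-20/-22: weighted mean -15, equal-country mean -18. Overall error is 2.3%.
- Small countries worse, -9/-24/-30: weighted mean -15, equal-country mean -21. Overall error is 1.6%.

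**6. Stratified risk difference.** Error is about 2.5-2.9% in every layout with a true patient-weighted difference of -15 points. Power at 85%/85% is 90.0-90.1% with 120 per arm in the three layouts checked.

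**The case against.** The rule is a fixed algorithm, written into the SAP and recorded in its change log, and the protocol does call for the interaction to be investigated. Under a common effect the test rarely fires, and the pre-test adds at most about one point to overall error in the layouts tabulated (3.7% against 2.8% at 90/30). The SAP also plans an identity-link GENMOD analysis and a bootstrap CI, both without the interaction, and itself concedes a potential bias in the derived difference. All of this stands. It limits the size of the problem, and a discrepancy in the interaction branch would be visible. But those two analyses are labelled robustness checks, and no rule says what happens if they disagree with the primary result.

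Three stronger readings are tempting and are not supported:

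- **That error is well above 2.5% whenever the test fires.** With equal countries and a common effect it is about 3-4% for 2 to 5 countries. When small countries do worse, overall error falls below 2.5%.
- **That error can reach something like 47%.** A layout of 80/20/20 with differences -24/-2/+8 does give that figure. However, it assumes a 32-point spread between countries, and the equal-country difference is then -6, well inside the margin. Much of the figure is a disagreement about which average is the target, and the documents name none.
- **That deleting the pre-test is sufficient.** The additive branch alone runs at 2.8-4.7% in the clearly unequal layouts.

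**Conclusion.** The concern holds in conditional form. The SAP lets an interaction test select the model and CI for the only confirmatory decision, a step the protocol does not provide for. In the selected branch the SE is too small once country sizes are clearly unequal. With equal or mildly unequal countries the effect on overall error is negligible. The inflation seen with clearly unequal countries comes partly from the pre-test and partly from the equal weighting and pseudo-count variance that both branches share. With real differences between countries the direction depends on whether the small countries do better or worse, and that result requires taking the patient-weighted difference as the target.

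All error rates rest on assumed country numbers and sizes, 120 per arm, and a 70% vs 85% null in the common-effect case. The defect in the method does not depend on those assumptions; its size does. Severity: should-fix.

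**What to change.** In SAP 3.2.1.1, remove the interaction pre-test from the primary analysis and pre-specify one primary result: the country-stratified Mantel-Haenszel risk difference, Σw_k(p_Tk - p_Ck)/Σw_k with w_k = n_Tk n_Ck/(n_Tk + n_Ck), with its stratified (Sato) two-sided 95% CI. Compare the lower limit with -15% and, if non-inferiority is shown, with zero. This replaces the LS-means and pseudo-count step in both branches, in the mITT analysis and its PP repeat.

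State that the target is the difference averaged over the enrolled country mix. Keep the interaction model for the by-country table already planned in the same section, and the additive logistic model as supportive. Record the change in SAP section 5, because Protocol 10.4.5 names logistic regression for the primary endpoint.

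The cost is SAP wording and a few lines of code. It needs no extra data or subjects, and 120 per arm remains enough.
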